**Social Media-Delivered Patient Education in Enhancing Type 2
Diabetics Self-Management and Attitudes During the COVID-19
Pandemic: a Randomized Controlled Trial in Taiwan**

ClinicalTrials.gov NCT04876274.

10/02/2022

Study background

The development of effective diabetes education program in patients' self-management had been a challenge for healthcare professionals. The complicated pathology in diabetes required management not only on pharmacotherapy, but also patients' engagement in daily self-care. Previous studies demonstrated that patients with better disease-related knowledge, attitudes, practice and self-efficacy was associated with better glycemic control [1]. However, it was extremely difficult for patient to maintain the healthy life-style and self-management. The limited time and the health-care manpower in clinical settings became the main barrier to deliver proper diabetes education. The worldwide increasing prevalence rate of diabetes reflected the unmet needs in health education which called for an innovative and effective educational program.

The contents of diabetic education were very complicated as demonstrated by Diabetes Self-Management Education and Support (DSMES) and the American Association of Diabetes Educators 7 self-care behaviors (AADE7TM). To cover all aspects required in day-to-day living with diabetes, the education was recommended to include healthy eating, regular physical activity, self-monitoring of blood glucose (SMBG), compliance with medications, problem-solving skills, healthy coping skills, and other risk-reduction behaviors [2]. It was theoretically proven to effectively enhance health outcomes [3-7], but it might not be efficient in the busy clinical settings. Previous study had reported the time needed for teaching diabetes self-care was around 4 hours per patient, which was not easy to achieve in clinical practice [8]. To addressed the pressure on face-to-face education burden, "remote" might be a potential key solution, which could be cooperated with the advancing technology.

Mobile health technology (mHealth) were increasingly being integrated into

health care to meet the demands of diabetic care. With the widespread adoption of technology services nowadays, application of mobile app and wireless sensors, including the text, multimedia messaging and patients' SMBG, was proven to be effective in enhancing health outcome, such as medication adherence, HbA1C and self-managements [9-13]. However, there had been no previous study developed diabetes educational program based on the social media with two-way communication.

Objectives

This study developed an educational program, Taipei Medical University-Line Oriented Video Education (TMU-LOVE), based on the AADE7™. The social media employed in the study was LINE (©LINE Corporation limited, Japan). It was one of the most popular and user friendly social media platform in Taiwan, with high acceptance up to 91.5% among the population above 50 [14]. The study aims were: (1) to evaluate the effectiveness of TMU-LOVE on A1C, knowledge, attitudes and self-care activities by observing the changes before and after intervention; (2) to study the impact of TMU-LOVE on change of knowledge for diabetes patient with high or low levels of health literacy; (3) to explore the association between diabetes patients' attitudes and self-care activities.

Design and methods

This randomized controlled trial (RCT) was carried out from July 2020 to Jan 2021. The study was conducted in the Endocrinology and Metabolism Clinic in Wan-Fang Hospital. Participants were randomly divided into either control or intervention

groups. The control group received usual care while the intervention group received usual care and TMU-LOVE health education. Data were collected at baseline and 12 weeks after enrollment. The study was approved by the Taipei Medical University Jointed Institutional Review Boards (TMU-JIRB No.: N201905088).

Inclusion Criteria

The patient met the following criteria were included if they

- (1) Type 2 DM
- (2) Age 20 or older
- (3) Had at least 1 HbA1C data in the past 6 months
- (4) Possessed a smart-cellphone
- (5) HbA1C $\geq 6\%$

Exclusion Criteria

The patients were excluded if they had:

- (1) Gestational diabetes
- (2) Cognitive impairment
- (3) No medication treatment but dietary control alone

Control Group

Patients in the control group received usual health care, including outpatient services with physicians, nurses and pharmacists. The consultation by certified diabetes educators (CDE) was referred by physicians as needed.

Intervention Group

In addition to usual health care, patients in the intervention group were asked to join

the TMU-LOVE education platform.

Sample Size Calculation

The sample size of this study was estimated using G-power (version 3.1, Heinrich-Heine-Universität Düsseldorf, Germany). Assuming a power of 80% with a two-sided alpha level for detecting the difference between the intervention group and the control group, at least 64 patients were needed for each group. Considering a 20% dropout rate, the study was designed to have at least 80 patients for each group, 160 patients in total.

Randomization

Patients were randomized in a 1:1 ratio according to the random allocation sequence generated prior to the study. Patients with odd numbers were allocated to the control group while even numbers were allocated to the intervention group. The trial was non-blinded because of its feasibility.

Program description

With advantages of social-media integration, TMU-LOVE was conducted as a platform using LINE. It allowed for a one-on-one chat room, graphic messages, and the ability to steer customers to certain websites [15]. The study created a graphic menu which was composed of six parts, including understanding diabetes, daily care, nutrition care, diabetes drugs, quizzes, and questions and answers (Q&A). Patients could click on the menu for corresponding information. The messaging feature of TMU-LOVE also allowed researchers to send educational videos and communicate with patients by text message, or voice or video call. Patients could ask questions, and the research team would response with a suitable explanation via TMU-LOVE.

The content of TMU-LOVE included 51 diabetes educational videos according

to the seven key points in AADE7™ [2]. The videos were produced by undergraduate students in the School of Pharmacy, Taipei Medical University (TMU) and then verified by two pharmacists. Each video lasted 2~3 minutes, and videos were divided into five categories: 10 on understanding diabetes, 10 on daily care, six on nutrition care, 21 on diabetes drugs and four on diabetes knowledge-related quizzes. There were 21 diabetes drug videos based on the formulary at Wan Fang Hospital, including metformin, acarbose, dipeptidyl peptidase-IV (DPP-IV) inhibitors, meglitinide, sulfonylurea, thiazolidinedione, sodium-glucose cotransporter-2 (SGLT2) inhibitors, and insulin. All of the videos are listed in Multimedia appendices 1 and are also available at the website of the TMU School of Pharmacy [16].

The program was designed for a 12 week duration, with two or three videos sent every week and a care message sent every 2 weeks to patients in the intervention group. All patients received the same videos except those for medications. Videos regarding a basic understanding of diabetes were arranged firstly in weeks 1~4. Those for daily care were begun from week 5, with six nutrition care videos scheduled in 6 different weeks. Each patient received the videos for their individual medications in weeks 4, 6, 7, 11, and 12. There were four quizzes scheduled in weeks 3, 6, 9, and 12. Patients could also access to all videos through TMU-LOVE whenever they wanted.

Data collection

Questionnaire assessments in this study included A1C, patients' knowledge about diabetes, self-care activities, attitudes towards diabetes and health literacy. All data would be assessed at baseline and 12 weeks after enrollment except for health literacy. Questionnaire utilized in this study composed of 5 parts, including personal information, Simplified True / False version of Diabetes Knowledge Scale (SDKS) [18], Summary of Diabetes Self Care Activities (SDSCA) [20], Diabetes Care Profile-

Attitudes Toward Diabetes Scales (DCP-ATDS) [18] and Newest Vital Sign (NVS) [23].

Patients' knowledge about diabetes was measured by True / False version of SDKS. It contained 24 items and was validated in previous studies [17,18]. The measurement of patients' self-care activity was done by using SDSCA, which consisted of 10 items. It asked patients how many days per week did they had performed the right behavior regarding to medication adherence, diet, exercise, self-monitoring blood glucose and foot care. Its validity was proven in previous studies [19, 20]. Patients' attitude towards diabetes was assessed by questionnaire DCP-ATDS, which was previously validated and translated [18, 21]. It contained 17 items which could be divided into positive attitude, negative attitude, self-care ability, self-care adherence and importance of care. Each item was five-point Likert scale as graded for strongly agree, agree, neutral, disagree and strongly disagree. For assessment of health literacy, we used NVS, which was developed and translated in previous studies [22, 23]. It consisted of 6 questions designed based on an ice-cream nutrition label to evaluate both the reading and numeracy level of patients.

Statistical analysis

Statistical analyses were conducted using SPSS (SPSS, Released 2009. PASW Statistics for Windows, ver. 28.0. Chicago, IL, USA). The study was performed by intention-to-treat analysis. Multiple imputation was employed to manage the missing values. All tests were two-tailed, with a significance level of 0.05. Differences in baseline characteristics were examined using descriptive analysis. The Kolmogorov-Smirnov (KM) test was used to verify whether the variables had normal distributions. According to the results of KM test, a Wilcoxon signed rank test or paired t-tests were

used to examine the differences in the pretest and post-test scores within a group, while a Mann-Whitney test or unpaired t-tests were performed to compare the differences between groups. An ordinal logistic regression model was applied to evaluate the association of health literacy with knowledge, attitudes, and self-care activities.

References

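### The between-arm tests use baseline scores only as change scores, if at all; regression on arm and baseline is more precise at no data cost, and the odd/even number needs defining

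*Combined protocol and SAP*

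**What the plan says.** **Analysis.** The first aim in Objectives is to judge effectiveness on A1C, knowledge, attitudes and self-care "by observing the changes before and after intervention". Data collection says: "All data would be assessed at baseline and 12 weeks after enrollment except for health literacy". Each of the four outcomes therefore has its own baseline value. Under Statistical analysis, the comparison between arms is an unpaired t-test or a Mann-Whitney test, chosen by a normality test. The section says these compare differences between groups. That may mean differences in 12-week scores or, read with the first aim, in pre-post changes. No baseline covariate is named. Missing values are multiply imputed and the analysis is by intention to treat. For baseline: "Differences in baseline characteristics were examined using descriptive analysis".

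**Allocation.** Under Randomization, patients are randomised 1:1 "according to the random allocation sequence generated prior to the study". The next sentence reads: "Patients with odd numbers were allocated to the control group while even numbers were allocated to the intervention group". The section closes with: "The trial was non-blinded because of its feasibility". Design and methods adds only that participants were divided at random.

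**The concern.** The trial measures every outcome before and after, then compares the arms with a test that either discards the first measurement or uses it only by subtraction. Comparing 12-week scores gives up the precision that a correlated baseline offers. Subtraction adds noise when the correlation is low. Both leave a chance baseline imbalance in the estimate: 12-week scores carry part of it forward, and change scores over-correct for it. With about 64 evaluable patients per arm, the loss of power can be material.

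The allocation text leaves a smaller question. The number whose parity decides the arm is not defined, and neither custody of the sequence nor the timing of its release is described. In an open trial with questionnaire outcomes, a reader will want to know this.

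**Working it through.** **1. Inputs and the plan's own figure.** Sample Size Calculation gives 80% power, a two-sided test, 64 per arm, 20% dropout, and 80 per arm (160 in total). Alpha 0.05 comes from Statistical analysis. No effect size is stated. A two-sample t-test for 0.5 SD needs 63.77, so 64, per arm; 64/(1 − 0.20) = 80; 2 × 80 = 160. Solving back from 64 gives 0.499 SD. The figure reproduces if 0.5 SD was the target, which is an assumption.

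**2. Residual variance.** Assume the same SD (set to 1) at baseline and 12 weeks, and a linear relation with correlation r. The documents give no r, so 0.3, 0.5 and 0.7 are shown.

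| r | 12-week score: 1 | Change: 2(1 − r) | Adjusted: 1 − r² | Adjusted ÷ 12-week | Adjusted ÷ change |
|---|---|---|---|---|---|
| 0.3 | 1 | 1.40 | 0.91 | 0.91 | 0.65 |
| 0.5 | 1 | 1.00 | 0.75 | 0.75 | 0.75 |
| 0.7 | 1 | 0.60 | 0.51 | 0.51 | 0.85 |

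**3. Power at 64 per arm, true difference 0.5 SD of the 12-week score.** Standardised difference d = 0.5/√variance; noncentrality = d × √(64/2) = 5.657d; noncentral t, 126 df. The one degree of freedom spent on the covariate does not change the rounded results.

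| Analysis | r = 0.3 | r = 0.5 | r = 0.7 |
|---|---|---|---|
| 12-week score | d 0.500, 80% | d 0.500, 80% | d 0.500, 80% |
| Change score | d 0.423, 66% | d 0.500, 80% | d 0.645, 95% |
| Adjusted | d 0.524, 84% | d 0.577, 90% | d 0.700, 98% |

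**4. Sensitivity.** For a true difference of 0.3 SD, power is 39.1% for 12-week scores, 29.6%/39.1%/58.5% for change scores and 42.3%/49.4%/65.5% adjusted. If the 0.5 SD is instead in units of the SD of change, power is 91.3%/80.1%/58.5%, 80.1% throughout, and 93.6%/90.0%/86.1% respectively. The adjusted analysis is highest in every case.

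**5. Chance imbalance under valid randomisation.** The SE of a baseline gap is √(2/64) = 0.177 SD, so a gap of 0.2 SD or more in either direction occurs in 25.8% of trials on any one measure (20.6% at 80 per arm, SE 0.158). Given a chance gap of 0.2 SD, the expected shift in the 12-week comparison is r × 0.2 = 0.06/0.10/0.14 SD. In change scores it is (1 − r) × 0.2 = 0.14/0.10/0.06 SD in the opposite direction. After adjustment it is zero.

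**6. What adjustment does not do.** Suppose selection created a stable gap of 0.3 SD (an assumption) at 80 per arm and r = 0.5. The adjusted shift is 0.3 × (1 − 0.5)/√0.75 = 0.173, and the false-positive rate is 19%, not 5%. If the gap appeared only at follow-up, the shift is 0.3/√0.75 = 0.346 and the rate is 59%.

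**7. Allocation text.** Three readings fit the words:
- Parity decodes concealed, independently drawn random numbers. Allocation is valid, and the next arm is guessed right 50% of the time.
- The number is consecutive enrolment order. Allocation alternates, and the next arm is always known.
- Recruiters could see the random list. Allocation is random, but the next arm is always known.

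The first fits most naturally, because the parity sentence directly follows the one citing a random sequence. Nothing in the documents points to a visible list; that reading rests on silence.

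**The case against.** The planned tests are valid under randomisation and easy to explain. If the differences are change scores, baseline is already used. The gain also depends on an r that the documents do not give: at r = 0.3 it is about 4 points over 12-week scores, and at r = 0.7 about 2 to 3 points over change scores. The plan falls back on Mann-Whitney for non-normal data, which ordinary regression does not mirror. SDSCA and DCP-ATDS may yield several scores each, so there could be more than four models.

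All of this stands, and it makes the point an improvement in efficiency rather than the correction of an invalid analysis. It does not remove the advantage: the adjusted model is ahead in every case calculated, and it spares the plan a choice between two comparisons whose ranking depends on r.

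Two stronger inferences are tempting. A reader might conclude that allocation was alternation, or foreseeable and therefore biased. The documents do not support that: they cite a random sequence generated in advance, which parity can legitimately decode, and nothing shows bias. A reader might also conclude that the baseline table is uninformative about selection. That is too absolute. At 80 per arm, a t-test on one measure would flag a gap of 0.3/0.4/0.5 SD in 47%/71%/88% of trials. The plan names no baseline test, and an unremarkable table would not prove concealment, but the table is not worthless.

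**Conclusion.** The point holds as an improvement that needs no new data. The planned between-arm tests make no use of baseline values, or use them only through change scores. Regression on arm and baseline raises power to 84%/90%/98%, from 80% for 12-week scores and 66%/80%/95% for change scores. This rests on 64 evaluable per arm, an assumed 0.5 SD difference, equal SDs at the two visits, a linear relation, and assumed r = 0.3/0.5/0.7. The benefit is precision and protection from chance imbalance. It is not a remedy for foreseeable allocation, should that have occurred.

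The undefined odd/even number is a gap in reporting. It does not establish a quasi-randomised trial, and parity is not in itself a defect.

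**What to change.** **Analysis.** State that each 12-week outcome (A1C, SDKS, SDSCA, DCP-ATDS) is analysed by linear regression on arm and its own baseline value, pooled over the planned imputations. Report the adjusted between-arm difference with its 95% CI. Use robust or bootstrap standard errors if residuals are clearly non-normal. Say whether each SDSCA and DCP-ATDS analysis uses a total or its components.

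**Reporting, secondary.** Say what the odd/even number was, who held the sequence, and when the arm was revealed relative to consent and the baseline questionnaires. Describe the trial as quasi-randomised only if the numbers were consecutive enrolment numbers.

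**Cost.** No new data. Four models if each scale has one score. If the five SDSCA behaviours and five DCP-ATDS divisions are analysed separately, 1 + 1 + 5 + 5 = 12 models. The allocation details need a few sentences. Because "This randomized controlled trial (RCT) was carried out from July 2020 to Jan 2021", none of this changes how patients were allocated.

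### Multiple imputation is combined with a normality-gated choice of test and no pooling rule, so the intention-to-treat p-value is not uniquely defined

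*Combined protocol and SAP*

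**What the plan says.** The Statistical analysis section commits to intention-to-treat and then states "Multiple imputation was employed to manage the missing values". It also states "All tests were two-tailed, with a significance level of 0.05". A Kolmogorov-Smirnov test decides whether each variable is treated as normal. Within groups this leads to a Wilcoxon signed rank test or a paired t-test. Between groups, "a Mann-Whitney test or unpaired t-tests were performed to compare the differences between groups".

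Four things are not stated: the variables in the imputation model, the number of imputations, the rule for combining results, and whether the normality test is run on observed or imputed values.

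The only figure on missing data is the allowance under Sample Size Calculation: "Considering a 20% dropout rate, the study was designed to have at least 80 patients for each group, 160 patients in total".

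**The concern.** Multiple imputation produces several completed data sets. Rubin's rules combine them through an estimate and its standard error from each. A t-test supplies both. Mann-Whitney and Wilcoxon tests as usually reported supply a rank statistic and a p-value, so an analyst who reaches the rank branch must choose how to combine them, and the plan does not say how.

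The gate adds a second gap. Each imputed data set has different filled-in values, so the normality verdict can change from set to set. One outcome could then be tested by t-test in some sets and by Mann-Whitney in others, with no rule to reconcile them.

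The rank branch is a realistic route. The Data collection section describes a 24-item true/false knowledge scale, self-care items counted in days per week, and five-point attitude items. These are bounded, discrete scores of a kind that normality tests often reject. At stake is the effectiveness comparison in the first study aim: several p-values would be consistent with the text, and the choice could be made after seeing them, in a trial that was not blinded.

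**Working it through.** **Inputs from the documents.** Two-sided 0.05 (Statistical analysis; the sample-size text gives no alpha value), 80% power, 64 evaluable and 80 enrolled per group, 20% dropout, 1:1 allocation, assessments at baseline and 12 weeks.

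**Assumptions not in the documents.** Effect size 0.5 SD, baseline-to-week-12 correlation r, number of imputations M, values missing completely at random, and normal-regression imputation from baseline within each arm.

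**The plan's own figure.** The normal approximation gives n = 2(1.960 + 0.842)²/0.5² = 62.8, so 63. The exact two-sample t-test gives 63.77, so 64, with power 80.1%. Then 64/(1 − 0.20) = 80. The stated sizes are reproduced if the effect is 0.5 SD. At the full allowance, 0.20 × 80 = 16 week-12 values per arm would be imputed.

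**Pooling.** For estimates Q₁…Q_M with variances U₁…U_M, Rubin's rules use the mean of the Q's, the mean variance W, the between-imputation variance B = Σ(Q_m − Q̄)²/(M − 1), and total variance T = W + (1 + 1/M)B. This works with Q as the mean difference, and equally with Q as the Mann-Whitney probability P(X>Y) and its variance. Using one imputed set, averaging the imputed values, or taking the median p-value does not carry B into the test.

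**False-positive rates (%) with no true effect, 80 per arm.** The first three result columns use Mann-Whitney. M = 5 with 2,500 trials, except the M = 20 row (1,500 trials).

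| Setting | One set | Averaged values | Median p | P(X>Y), Rubin | Mean difference, Rubin |
|---|---|---|---|---|---|
| 20% missing, r = 0.5 | 8.4 | 9.9 | 6.7 | 4.3 | 4.3 |
| same, M = 20 | 8.6 | 10.5 | 6.9 | 4.2 | 4.1 |
| 20%, r = 0.2 | 10.3 | 12.6 | 8.3 | 4.8 | 4.3 |
| 20%, r = 0.8 | 6.8 | 7.0 | 6.0 | 4.9 | 4.8 |
| 20%, r = 0.5, change score | 9.4 | 10.8 | 8.0 | 5.3 | 5.3 |
| 20%, r = 0.8, change score | 10.3 | 12.7 | 8.2 | 5.2 | 4.8 |
| 20%, skewed data | 8.3 | 9.6 | 6.1 | 3.7 | 3.8 |
| 10%, r = 0.5 | 7.4 | 7.4 | 6.4 | 5.5 | 5.3 |
| 5%, r = 0.5 | 5.4 | 5.6 | 5.4 | 4.9 | 4.7 |
| 20%, arm left out of imputation | 4.6 | 4.4 | 3.3 | 1.9 | 2.2 |

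Simulation error near 5% is √(0.05 × 0.95/2,500) = 0.44 points.

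**Rank test against t-test.** A separate base-case run gave, for t-test and Mann-Whitney respectively: one set 9.5% and 8.8%; averaged values 9.6% and 10.2%; median p 7.3% and 7.6%. The excess is about the same for both.

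**Stability of the gate.** The Lilliefors form of the test was run in each arm, with M = 5, 20% missing and 400 trials per setting. The verdict differed between imputed sets in 20% of trials for normal data, 21-50% for skewed data, and 64% for whole-number scores with continuous imputations. A different set-up, testing the change score with both arms together on a 0-24 whole-number scale, gave 35-41%.

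**Stability of the conclusion.** Some imputed sets gave Mann-Whitney p < 0.05 and others did not in 15-28% of trials with no effect, and in 23-36% at a true 0.5 SD effect.

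**The case against.** A reader might infer that rank tests cannot be pooled after imputation, so that no valid p-value exists. That goes too far. P(X>Y) has a standard error and pools by Rubin's rules, and the t-test branch pools directly. With imputation by arm, the two Rubin columns stay between 3.7% and 5.5%. What is missing is the rule, not the possibility.

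A reader might also infer that the trial's false-positive rate is about 7-11%. The documents do not support this. No section says that one imputed set, averaged values or a median p-value was used. The excess comes from ignoring between-imputation variance and affects t-tests about equally, so the rank test is not its cause. It also depends on the setting: averaging the p-values gave 4.9% in the base case, and leaving arm out of the imputation model removed the excess. That omission is no remedy, because imputed values would then carry almost no arm difference and would dilute the effect.

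Other parts of the objection stand. The 20% is a sample-size allowance, not observed missingness. The gate may have been run once on observed data, in which case it cannot disagree with itself, although pooling on the rank branch would remain undefined. The simulations applied Mann-Whitney in every trial rather than only after a failed normality check, so they describe the test and not the whole gated procedure. In most trials the imputed sets agreed on significance. Finally, preferring a mean difference to a rank comparison changes what is estimated.

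**Conclusion.** The concern holds as a gap in specification. The plan does not lead to one defined test and one defined p-value per outcome once values are imputed, because the pooling rule and the data used for the gate are both unstated. If the gate is run on imputed data, conflicting test choices are common: roughly 20% of simulated trials for normal data and 35-64% for whole-number scores.

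Inflation is a risk that depends on what the analyst did. With about 20% missing and arm in the imputation model, the three shortcuts gave 6.0-12.7% for rank tests, with a similar excess for t-tests in the base case. At 5% missing they gave 5.4-5.6%. These sizes rest on the assumed correlation, number of imputations, random missingness and imputation model. The documents establish neither that a shortcut was taken nor that rank results are beyond valid pooling. This is a cheap improvement rather than a correction on which the trial's validity depends.

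**What to change.** Drop the normality gate and name one between-group estimator in advance for each of A1C, SDKS, SDSCA and DCP-ATDS. A suitable choice is the difference in mean 12-week value or change, preferably adjusted for baseline, with a robust standard error if needed. Include arm, baseline values and NVS in the imputation model, and state the number of imputations. Estimate the difference and its standard error in each imputed set, pool by Rubin's rules, and report the pooled difference, 95% CI and p-value. Keep Mann-Whitney as a sensitivity analysis on observed data, or pool it through P(X>Y).

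The Design and methods section places the trial between July 2020 and January 2021, so the revised text should say that this estimator was fixed after data collection.

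The cost is a few sentences and a re-run on data already held. The result becomes a mean difference rather than a rank comparison, and p-values may be slightly less favourable than those from an unpooled shortcut, if one was used.

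### The plan does not say that the between-arm comparison decides effectiveness, so a within-arm pre/post p-value could be used to claim benefit

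*Combined protocol and SAP*

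**What the plan says.** Under Objectives, the first aim is "to evaluate the effectiveness of TMU-LOVE on A1C, knowledge, attitudes and self-care activities by observing the changes before and after intervention". The control arm is not named there as the comparator.

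The Statistical analysis section gives two families of tests in one sentence. Paired t or Wilcoxon signed rank tests are "used to examine the differences in the pretest and post-test scores within a group". The sentence then continues: "while a Mann-Whitney test or unpaired t-tests were performed to compare the differences between groups". It does not say whether the between-group tests use change scores or 12-week scores. One general rule covers everything: "All tests were two-tailed, with a significance level of 0.05". No primary outcome or primary analysis is named, and nothing states that the paired tests are descriptive.

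The Sample Size Calculation section refers to one contrast only: "Assuming a power of 80% with a two-sided alpha level for detecting the difference between the intervention group and the control group".

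**The concern.** A paired test inside one arm asks whether that arm changed over 12 weeks. It does not ask whether TMU-LOVE caused the change. Both arms receive usual care, which may include referral to a diabetes educator, and both complete the same questionnaires twice. Either arm can therefore change for reasons unrelated to the programme. Finding significance in one arm and not in the other does not test the difference between them, because two arms with the same true change can easily fall on opposite sides of 0.05.

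Read literally, the wording of Aim 1 is closer to the paired test than to the between-group test. With no stated order between the two, a report that follows the plan could rest its main conclusion on a within-arm p-value and lose what randomisation provides.

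**Working it through.** **Inputs from the documents.** Two-sided 0.05 (Statistical analysis); 1:1 allocation (Randomization); 80% power, 64 per group, 20% dropout, 80 per group and 160 in total (Sample Size Calculation).

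**Assumptions, because the documents give no figure.** A standardised difference of 0.5 in step 1. In steps 2 to 4, a common true change δ in both arms, in SDs of the change score, from 0 to 0.5; normally distributed changes; independent arms. Only the t-test branch is calculated.

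**Step 1: the plan's own figure.** A two-sample t-test with two-sided 0.05, 80% power, 1:1 allocation and an assumed difference of 0.5 SD gives n = 63.77, rounded up to 64 per group (power at 64 is 80.1%). Dropout: 64 / (1 − 0.20) = 80 per group, and 2 × 80 = 160. The stated size therefore fits a two-arm comparison, which agrees with the plan's own description of it.

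**Step 2: the paired test in one arm.** The probability p of a significant improvement is P(T > t), where t is the 97.5th percentile of the t distribution with n − 1 degrees of freedom and T is noncentral t with noncentrality δ√n. For n = 64, √n = 8, so δ = 0.25 gives noncentrality 2.0 and p = 0.504.

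**Step 3: the misleading pattern.** With the same δ in both arms there is no treatment effect. The probability that the intervention arm improves significantly and the control arm does not is p(1 − p). At δ = 0.25 this is 0.504 × 0.496 = 0.250, which is the maximum because p(1 − p) cannot exceed 1/4.

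| Common change δ (SD) | Noncentrality, n = 64 | p, n = 64 | p(1 − p), n = 64 | p(1 − p), n = 80 |
|---|---|---|---|---|
| 0 | 0 | 0.025 | 0.024 | 0.024 |
| 0.1 | 0.8 | 0.121 | 0.106 | 0.121 |
| 0.2 | 1.6 | 0.350 | 0.228 | 0.244 |
| 0.25 | 2.0 | 0.504 | 0.250 | 0.240 |
| 0.3 | 2.4 | 0.657 | 0.225 | 0.185 |
| 0.4 | 3.2 | 0.883 | 0.103 | 0.054 |
| 0.5 | 4.0 | 0.976 | 0.023 | 0.007 |

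The last column is for all 80 per arm, the number that would enter an intention-to-treat analysis with imputation. The picture is similar, with the peak at a slightly smaller change.

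**Step 4: the between-arm test.** The true difference is 0 whatever the value of δ, so a two-sided 0.05 test favours the intervention in 2.5% of trials. In 40,000 simulated trials per setting, the two-sided rejection rate was 4.8% to 5.2%. At n = 64 and δ of 0, 0.2, 0.25, 0.3 and 0.5, the simulated rates of the pattern in step 3 were 0.025, 0.226, 0.248, 0.227 and 0.023, in line with the formula.

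**The case against.** The strongest reply is that the right comparison is already in the plan. The same sentence that lists the paired tests also lists between-group tests, and the sample size is for that contrast alone. Aim 1 can be read as measuring each patient's change and then comparing changes between arms. The 0.05 sentence is a general convention, not a decision rule. This stands, and it limits the point to a missing statement of which test decides.

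A reader might infer that the plan's own false-positive rate is raised to the figures in the table. The documents do not support that: no section says that TMU-LOVE will be declared effective on a within-arm p-value. The table shows what such a use would cost, not what the plan commits to.

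A reader might also combine the pattern over A1C, knowledge, attitudes and self-care to obtain a much larger figure. That would require independent outcomes, all with a common change near the peak, and would mix in multiplicity, which is a separate matter. Nor does the point need regression to the mean from the HbA1C entry threshold: no A1C distribution is given, and the threshold does not select directly on the questionnaire scores.

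Finally, it can be said that naming the between-arm test as decisive is enough and that ANCOVA is a preference. It is true that the statement of precedence cures this fault. ANCOVA is recommended because the baseline values are already collected and because the present wording leaves open which scores the between-group test uses.

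**Conclusion.** The point holds as an ambiguity with consequences, not as a missing analysis. The between-arm comparison is planned and sized for, but Aim 1 and the unranked list of tests leave room to claim benefit from within-arm results.

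With 64 per arm, one outcome and an identical true change in both arms, significance in the intervention arm only occurs in about 2% (0 SD), 11% (0.1), 23% (0.2), 25% (0.25), 23% (0.3), 10% (0.4) and 2% (0.5) of trials, against 2.5% for a between-arm test wrongly favouring the intervention. At 0 and at 0.5 SD this pattern is no more frequent than the between-arm error. At 0.5 SD, however, a paired test read alone in the intervention arm would be significant in 98% of trials. All these figures depend on the assumed common change. The conclusion that a within-arm test cannot isolate the programme's effect does not.

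**What to change.** - **Objectives:** reword Aim 1 as a comparison of A1C, knowledge, attitudes and self-care between arms at 12 weeks.
- **Statistical analysis:** state that effectiveness is judged only on the between-arm difference at 12 weeks, estimated by ANCOVA adjusted for the baseline value of the same outcome, with its 95% CI. For clearly non-normal outcomes, use a rank-based or bootstrap version of the same comparison.
- **Within-arm changes:** report them descriptively, without p-values, and state that they are not evidence of effectiveness. That statement matters more than the format, since a within-arm interval that excludes zero invites the same misreading.

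**Cost.** A few sentences of wording and the loss of the within-arm p-values. No new patients, visits or data are needed, and the sample size stands because it is already described as being for the between-arm difference. The Design and methods section says the trial ran from July 2020 to January 2021, and the document is dated 10/02/2022. If the change is made after the data were seen, it must be labelled post hoc.
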